Post-operative comparison between standard gradient compression dressing vs.
NonCompressive Bioactive Garment on pain, swelling and range of motion following total knee
arthroplasty.

NCT04751942

08-09-2021

PROTOCOL TITLE:

Post-operative comparison between standard gradient compression dressing vs. NonCompressive Bioactive Garment on pain, swelling and range of motion following total knee arthroplasty.

PRINCIPAL INVESTIGATOR:

[name]

[contact]

[contact]

Objectives

This prospective study will evaluate pain, swelling, ROM as well as narcotic use in postoperative total knee arthroplasty patients using novel Non-Compressive Bioactive Garment (NCBG) versus current standard of care gradient compression stocking (Thrombo-EmolicDeterrent or TED hose). If NCBG proves to be more effective in these outcome areas, it will provide a new and comfortable way to reduce patient pain and swelling immediately following surgery.

Background

Total knee arthroplasty (TKA) is one of the most popular surgical procedures today. It is designed and proven to effectively reduce pain caused by end-stage osteoarthritis. Despite its achievements, up to 25% of patients remain dissatisfied after the procedure due to lingering pain, amongst other complaints. Post-operative swelling of the knee and leg is thought to be a contributor to this persistent pain.

Traditionally, a standard gradient compression stocking is applied to the knee and leg after surgery to reduce this pain and swelling. However, due to ineffectiveness or patient noncompliance, compression stockings are often not entirely successful at preventing edema. The recently developed NCPS is a lower extremity garment comprised of a technical fabric that is thought to be able to prevent edema and reduce pain all in a comfortable, user-friendly manner. The purpose of this study is to determine if the NCPS is effective at improving post-operative pain, swelling, ROM and analgesic use associated with TKA.

Pain and prolonged recovery time associated with post-operative swelling are two factors that contribute to patient dissatisfaction following TKA. Swelling of the knee following TKA is caused by intraarticular bleeding and inflammation of the periarticular tissues, which can lead to a decrease in functional performance including pain and delayed rehabilitation. In a study by

Noble et al, 1/3 of dissatisfied patients reported that their knees swelled at least once per week, leading to pain and discomfort¹. Decreased quadriceps strength following knee surgery has been shown to prolong recovery¹⁻⁸. Fahrer et al showed that knee effusions inhibited reflex neurons and altered kinetics and muscle activity in quadriceps, which ultimately causes decreased strength². Holm et al later showed us that knee swelling played a part in post-operative quadriceps strength following TKA³. Ultimately, if post-operative swelling can effectively be reduced, patient recovery could be expedited and patient satisfaction could be improved.

Compression stockings have been utilized to attempt to reduce post-operative swelling. Compression works to prevent swelling by reducing the hydrostatic pressure in the leg. Reducing hydrostatic pressure prevents the capillaries from oozing and allows blood to move freely from the superficial to the deep venous system, subsequently allowing excess fluid to flow away from the interstitial space⁹.

More recently, the use of gradient compression stocking following TKA has come into question for its efficacy. While the application of external pressure from these gradient compression stocking is beneficial for a period, they are often unable to exert a sufficient amount of pressure long enough to prevent painful edema for an extended amount of time. A study by Bowling et al showed that these garments showed sufficient compression during the first few hours after surgery, but the pressure they applied dropped with time and required daily measurements and refitting to maintain appropriate and therapeutic compression¹⁰. This poses a problem not only medically, but financially as well. These compression stockings lose their fit so quickly, new ones must be prescribed frequently, leading to costly bills for the patient. It's clear that compression stockings are not as effective as once thought when it comes to controlling pain and swelling post-operatively.

A potential solution to the problems posed by traditional compression stocking is the NCPG. The garment is comprised of a semi-conductive material ground to nanoparticles that are embedded into the fibers, formed into a three-dimensional woven fabric for optimized comfort. Instead of relying on compression, NCPS utilizes the body's own thermal energy to generate infrared energy. The infrared energy generated is reflected back at the body and modifies cellular activity at the level of the mitochondria through a process known as photobiomodulation¹⁴⁻¹⁵. This process of photobiomodulation is hypothesized to improve swelling and tissue healing by increasing the activity of mitochondria and the availability of cellular energy in the form of ATP.

This study seeks to determine if NCPS use of infrared energy is more successful at reducing pain and swelling following TKA than traditional gradient compression dressing

Inclusion and Exclusion Criteria

	Inclusion Criteria
1.	Age range: from 18 to 89
2.	Primary unilateral Total Knee Replacement - Cruciate retaining and Posterior stabilized designs

	Exclusion Criteria
1.	Leg circumference > 23 in.
2.	Allergy to silicone/polyester
4.	Current, previous DVT
5.	Primary Inflammatory Type arthritis (i.e. rheumatoid arthritis)
6.	Inability to follow standardized post op and rehab protocols
7.	Lymphedema
8.	History of Vascular Bypass Surgery on Operative Limb ie) Fem-Pop or Fem-Fem
9.	Chronic Narcotic Use History
10.	Anticoagulation therapy (coumadin, rivaroxaban, apixaban)

Number of Research Participants

We will enroll 100 subjects throughout all sites involved in the study.

Recruitment Methods

Patients will be recruited in the office setting after all non-operative modalities for controlling pain associated with end-stage osteoarthritis of the knee have been exhausted. Patients will then be presented with the option of total knee replacement. After patient has agreed to undergo TKA, patients will then be asked (in a face-to-face setting) if they would like to participate in the study.

Setting

Research procedures will be conducted in the following locations:

- Geauga Medical Center in Chardon, OH
- Beachwood Medical Center, Beachwood, OH

Patients will be identified and recruited at office locations in Geauga and Beachwood, Ohio

Consent Process

Patients will be approached in the office setting after it has been determined that they have failed conservative management of advanced knee arthritis. Patients will be in the surgeons' clinic behind closed doors with the performing surgeon and another member of the research team. Consent will be obtained in the office after scheduling total knee arthroplasty procedure. The consent process is expected to take 30 minutes, but more time is available to ensure that patients have all their questions answered prior to signing the consent form.

Sharing of Results with Research Participants

- Results will not be shared with research participants
- Results will not be shared with research participants' doctors

Study Design

Prospective randomized control cohort study

Study Procedures

Patients will be enrolled in study prior to surgery, outlined above in the consent process.

At the time of patient enrollment, A trained member of the research team will measure the circumference of the patient's leg at the mid-thigh, mid-knee and mid-calf with the leg in full extension. The patient's range of motion of the operative leg will be measured in flexion and extension. The patient will also fill out a baseline Western Ontario and McMaster Universities Osteoarthritis Index (WOMAC) Questionnaire. All measurements and questionnaire answers will be recorded on the study data collection sheet and will be transferred to RedCAP. At this time, patient's will be assigned a unique study identifier which will be randomly assigned to the experimental or control group. Unique study identifier numbers will start at "#1" and will go up by one additional number with every patient enrolled in the study. Even numbers will be assigned to the control group and odd numbers will be assigned to the study group, ending with 50 people enrolled in each group.

The patient will then go on to have their primary total knee arthroplasty by standard of care procedure. Both cruciate retaining and posterior stabilized total knee replacement designs will be included in the study. Following closure of the surgical site and placement of a postoperative occlusive dressing, the operative leg will be measured once more for circumference and range of motion, and the values will be recorded on the study data collection sheet and transferred into redcap. The patient will then be placed in their randomized post-operative sleeve/device and will be transferred to the PACU and will receive the standard postoperative treatment.

Pre-operative, intra-operative and post-operative pain protocols will be uniform across performing surgeons and will include pre-operative adductor canal block, intra-operative posterior capsular injection of local anesthetic, and a standardized post-operative medication regimen consisting of:

- Percocet 5/325mg every 6 hours #28 pills
- Ibuprofen 800mg every 8 hours x 14 days
- Carisoprodol 250mg every 8 hours x 14 days
- Gabapentin 300mg every evening x 14 days

- Enteric Coated Aspirin 325mg every 12 hours x 28 days (for DVT prophylaxis)
- Ascorbic Acid 500mg every 12 hours x 14 days
- Colace 100mg every 12 hours for 7 days

On post-operative day one, patient's will be seen and evaluated in their inpatient rooms. Their leg measurements will be taken again with the knee sleeve/compressive gradient dressing pulled down. Measurements will be recorded on the data collection sheet and transferred to RedCAP. Patient's skin will be inspected for any reactions to the sleeve and a standard postoperative examination will be performed to ensure no neurovascular compromise, blood clots, infections or other post-operative complications. The number of oral narcotic pain medications consumed since time of surgery will also be recorded on the data collection sheet and transferred into RedCAP.

Patients will likely be discharged on post-operative day 1. Patients that have not been discharged on post-operative day 1 will not be measured on post-operative day 2.

Sleeves will be worn morning and night for 2 weeks, removing them only for hygiene and washing of the sleeve. After 2 weeks, the patient's will wear the sleeve as much as they can tolerate day and night. At 6 weeks, sleeves will be discontinued all together. Final ROM and Circumference Measurements will be obtained at 12 weeks post-operative mark.

Patients will be asked to fill out the WOMAC questionnaire at the time of consent, postoperative day 1 and at each subsequent post-operative visit.

Patients will be seen back at regularly scheduled post-operative visits of 2 weeks, 4 weeks, 6 weeks and 12 weeks. Patients will be given a WOMAC questionnaire to fill out at each visit. They will also give a numerical score for their perceived average pain level since their last visit. Patients will also be asked to bring in their narcotic pain pills to the post-operative appointment so they can be counted. The WOMAC questionnaire, leg circumference, knee range of motion, average pain score and number of remaining narcotic pain pills will be collected on the data collection sheet and transferred to RedCAP. Any complications will also be recorded.

The Reparel leg sleeve is the experimental device being investigated in this study. It is intended to improve swelling in the post-operative knee. Further description of the device is provided in the background section of this protocol

EPIC Electronic Medical Records will be used to collect data about patients during their inpatient, post-operative stay. Ambulatory EMR will be used in the outpatient setting to collect data and track post-operative clinic visits.

Study Timeline

	Pre-Screening	Time of Consent	Post-op	Post-op day 1	2 week post-op	4 week post-op	6 week post-op	12 week Post-op
Total Estimated time of visit	30 minutes	35 Minutes	5 minutes	30 minutes	30 minutes	30 minutes	30 minutes	30 minutes
WOMAC Questionnaire		x		x	x	x	x	x
Leg Circumference measurements		x	x	x	x	x	x	x
Knee Range-of-motion		x	x	x	x	x	x	x
Review of pain scale and narcotic use log				x	x	x	x	x

The enrollment period will be 1 year from the time of the first patient enrolled in the study. The enrollment period may be expanded to allow for the investigators to reach their goal of 100 patients. The total amount of time each patient will be involved in the study will be 12 weeks. Patients will only be required to wear the post-operative sleeve/dressing for 6 weeks post-operatively. Patients will continue to report their narcotic consumption and average pain scores for 12 weeks post-operatively.

Data to be Collected for your study (AFTER consent and HIPAA Authorization have been obtained)

Mid-thigh, mid-knee, and mid-calf measurements in extension
Range of motion measurements in knee flexion and knee extension
Western Ontario and McMaster Universities Osteoarthritis Index (WOMAC)
Visual analog Pain scale
Pain medications consumed
Adverse clinical events including DVT, stroke, PE, surgical site infection, reoperation Name
Medical record number
Patient demographics (age, sex, weight, height, BMI)

Data Analysis Plan

Demographics will be reported using descriptives such as count data and percentages. Differences between groups at baseline (pre-op) will be reported using two-tailed independent ttests for continuous variables, and chi-square or Fisher's Exact tests for categorical data, as appropriate.

The primary outcomes of range of motion, leg circumference, and pain ratings will be compared post-op between conditions using two-tailed independent t-tests. Should clinically relevant

demographics differ significantly between conditions pre-op (baseline), post-op comparisons will instead be conducted using one-way ANCOVAs controlling for differences at pre-op (baseline). These comparisons will additionally be made at multiple additional time-points throughout a 12- week post-op time period.

A priori power analyses were calculated for two-tailed independent t-tests for each primary outcome, using an alpha of .05, power = .80. Each of these are reported and the average of these numbers is used to calculate the final sample size. Clinically significant reductions in pain are defined as a 2-point change with a standard deviation of 2.5 using a 10-point scale; 84 patients were estimated. Clinically significant changes in range of motion are defined as: 10 degrees of difference from a 0-140 degree estimated range of values. Clinically significant changes in leg circumference are defined as: 1 cm difference in leg circumference using a 15-30 estimated range of values. To identify medium effect sizes of .55, 106 patients were estimated. Averaging these values, 99 patients were estimated. To ensure equal numbers of patients in each condition, 100 patients will be recruited for this study.

Risks to Research Participants

Patients will be monitored for allergic reactions and over compression leading to tourniquet effect. There is potential for the experimental garment to not be as effective as the TED hose, which would potentially increase swelling. There is risk of discomfort while wearing the experimental or standard of care garment. Breach of confidentiality is always a concern anytime there is large amounts of patient data being collected, but the risk is being minimized by use of locked storage cabinets for hard copy data and RedCAP for electronic recording of data. There are no perceived psychological, social, legal or economic risks associated with participation in the study. All normal post-operative complications and risks still apply to patients undergoing TKA. Risks associated with the use of the experimental device are expected to be incredibly rare, minor, short lived and completely reversible.

Provisions to Protect the Privacy Interests of Research Participants

Consent will be obtained in a private room at an outpatient clinic facility with solid doors. Consent will be done one-on-one with patients and with another trained members of the research team present in the room.

Potential Benefit to Research Participants

If sleeve is found to be an effective adjunct to decreasing swelling and increase knee ROM, patients will likely have less pain post-operatively and have potential for increased range of motion. If pain is better improved, patients may use less narcotic pain medication which could reduce risk of developing opioid dependence. Patient participation in the study has the potential to benefit society.

Withdrawal of Research Participants

Patients are able to withdraw from the study at any point in time. If this occurs we will use the data we have recorded if possible and the patient will be included in the withdrawn numbers of the study.

Alternatives to Participation

Patients are still free to undergo TKA without needing to participate in the study using the SOC gradient compression dressing

Costs to Research Participants

There is no additional cost to the patient. The standard TKA procedure and all associated costs will be billable to the patient's insurance company. The experimental knee sleeve will be provided to the patient at no cost. The standard of care gradient compressive dressing will be billed to the patient's insurance. Patients will be responsible for payment of provided services in the event of insurance denial. The Non-Compressive Bioactive Garment will be provided at no cost by Challenger Health, LLC (dba Reparel).

Research Participant Compensation

Patients will not be compensated for their participation in the study.

Provisions to Monitor the Data to Ensure the Safety of Research Participants

The data will be monitored every 10 patients to assess for completeness, accuracy and adherence to the protocol. We will also be monitoring for any obvious safety concerns that may arise.

[name], MD will be the designated Independent Medical Monitor who will review halting rules, advise the study team on safety oversight, evaluate adverse events and SAEs, review safety reports and protocols deviations related to safety, rights and welfare of patients.

Drugs or Devices

Non-Compressive Bioactive Garment– Reparel leg Sleeve Company Name: Challenger Health, LLC (dba Reparel) FDA Registration Number: 3012651665 Device Listing Number: D269770
Product Classification: Class I Medical Device, 510(k) exempt Product Code: FQL, Stocking/Medical Support

References:

1. Noble PC1, Conditt MA, Cook KF, Mathis KB. The John Insall Award: Patient Expectations Affect Satisfaction with Total Knee Arthroplasty. *Clin Orthop Relat Res.* 2006 Nov;452:35-43.
5. Hopkins J.T.: Knee joint effusion and cryotherapy alter lower chain kinetics and muscle activity. *J Athl Train* 2006; 41: pp. 177-184

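### The arm is fixed at the office enrolment visit although the garment goes on only after wound closure, which allows pre-exposure losses to use up allocated places and makes the arm knowable during surgery and at the post-closure measurement

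*Combined protocol and SAP*

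**What the plan says.** All references are to the combined protocol and SAP.

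- **Consent Process:** "Consent will be obtained in the office after scheduling total knee arthroplasty procedure". The discussion takes place "behind closed doors with the performing surgeon and another member of the research team".
- **Study Procedures, enrolment:** "Patients will be enrolled in study prior to surgery, outlined above in the consent process". After the baseline circumference, range of motion and WOMAC, "At this time, patient's will be assigned a unique study identifier which will be randomly assigned to the experimental or control group". Numbers run upward from 1 in order of enrolment, and "Even numbers will be assigned to the control group and odd numbers will be assigned to the study group". Enrolment continues under this rule, "ending with 50 people enrolled in each group".
- **Study Procedures, surgery:** "Following closure of the surgical site and placement of a postoperative occlusive dressing, the operative leg will be measured once more". This repeat measurement covers circumference and range of motion. Only then is the garment put on, before transfer to recovery. Analgesic protocols before, during and after surgery are to be the same for all surgeons.
- **Inclusion and Exclusion Criteria:** eligibility depends partly on the operation itself: "Primary unilateral Total Knee Replacement - Cruciate retaining and Posterior stabilized designs".
- **Withdrawal of Research Participants:** data already recorded are used where possible, and the patient is counted as withdrawn.

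The documents set no limit on the time from consent to surgery. They describe no eligibility re-check at surgery, no replacement of allocated patients who are not operated on, no analysis population, no dropout allowance, and no blinding of surgeon or assessor.

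**The concern.** Allocation comes before exposure by an interval of unstated length that contains the whole operation. Two things follow, and both would remain even with a sound random sequence if it were opened at the consent visit.

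First, the group sizes are counted at enrolment. A patient allocated in the office whose operation is cancelled fills one of the 50 places but can contribute nothing to the post-operative t-tests. Such a loss says nothing about the garment; it only shrinks the groups and may unbalance them.

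Second, the surgeon attends consent and then operates with the arm already fixed. The last measurement before the garment goes on is also taken with the arm fixed. Since the parity of the study number is the arm, anyone who sees the number knows the assignment. Range of motion and circumference are primary outcomes and depend on the measurer, so this is an opening for bias that can be closed cheaply.

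**Working it through.** **Order of events (Consent Process and Study Procedures)**

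1. Surgery is scheduled.
2. Consent in the office, with the performing surgeon present.
3. Baseline measurements.
4. Study number issued and arm fixed; the patient counts toward the 50 per group.
5. Operation, closure and dressing.
6. Post-closure circumference and range of motion.
7. Garment applied.

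The arm is needed only at step 7 but is fixed at step 4. The pre-operative baseline at step 3 is described before the number is issued. Steps 5 and 6 are the ones exposed to knowledge of the arm.

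**Inputs for the power check (Data Analysis Plan)**

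- Two-tailed independent t-test, alpha .05, planned power .80.
- Effect size d = .55, stated total 106.
- Pain: 2-point difference, standard deviation 2.5, so d = 2/2.5 = .80, stated total 84.
- Final total 100, so 50 per arm. The only reason given for going from 99 to 100 is equal arms.
- Loss between allocation and garment: not given. I assume 5-10% and show 20% as an outer case.

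**The plan's own figure.** For d = .55 the t-test needs 52.87 per arm, rounded up to 53, or 106 in total. This reproduces. The pain figure does not: d = .80 needs 26 per arm, or 52, and 84 corresponds to 95% power (42 per arm). That is a separate matter and does not affect this point.

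**Power after loss.** With n per arm, the noncentrality is d × √(n/2) on 2n − 2 degrees of freedom. Examples for d = .55:

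- n = 50: .55 × √25 = 2.75
- n = 45: .55 × √22.5 = 2.61

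| Assumed loss | Patients with outcomes | Mean per arm | Power, d = .55 | Power, d = .80 |
|---|---|---|---|---|
| 0% | 100 | 50 | 77.7% | 97.7% |
| 5% | 95 | 47.5 | 75.6% | 97.1% |
| 10% | 90 | 45 | 73.2% | 96.4% |
| 20% | 80 | 40 | 68.1% | 94.2% |

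At d = .55 a 5-10% loss costs 77.7 − 75.6 = 2.1 to 77.7 − 73.2 = 4.5 percentage points.

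**Consents needed if the 50 per group are counted at assignment.** N = 100/(1 − loss), rounded up:

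- 5%: 100/.95 = 105.3, so 106
- 10%: 100/.90 = 111.1, so 112

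That is 6 to 12 more consents than now, under the same assumption.

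**The case against.** A reader might infer more than the documents support, in four ways.

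- **That every change before surgery becomes a loss.** Only a cancelled operation necessarily leaves no post-operative data. A postponed patient is still operated on, and Study Timeline allows enrolment to be extended. A patient who starts an anticoagulant or receives another implant design could still wear the garment and be measured; nothing says such patients are removed. No third design is named as in use at these sites.
- **That control patients will leave more often.** Alternatives to Participation shows that the same dressing is available outside the study, and Costs to Research Participants shows that only the experimental sleeve is free. These make arm-related exit possible; they do not show that it happens. Nothing says patients are told their arm in the office.
- **That the surgeon is told the arm.** The documents do not say so. It is knowable, which is as far as the point goes.
- **That late assignment alone would cure this.** Under odd/even numbering the next arm can be predicted wherever the number is issued.

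Other objections carry weight. The uniform pain protocols, which cover the intra-operative capsular injection, narrow what a surgeon could do differently. Baseline is defined as pre-operative, and the post-closure value has no stated role as a covariate. Assessments on day 1 and at 2, 4, 6 and 12 weeks are unblinded whenever assignment is made. The power loss is small and could be met by enrolling more patients.

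What remains is this. Enrolling more does not hide the arm during surgery or at the post-closure measurement, and does not keep pre-exposure losses out of the allocated groups. The pain protocols govern analgesia, not the rest of the operation or the measuring.

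**Conclusion.** The point holds in a limited form. The plan fixes the arm earlier than it needs to. This **allows** losses before exposure that count toward the 50 per group, and it leaves the arm **knowable** during surgery and at the post-closure measurement. The documents do not establish that losses will occur, that they will differ by arm, or that anyone will act on the assignment. Losses would bias the comparison only if they, or exclusions because of them, differed by arm; otherwise they cost power and balance.

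The power cost is modest and rests wholly on an assumed 5-10% loss: from 77.7% to 75.6-73.2% at d = .55. For pain at d = .80, power stays at 96.4% or more over the same range. The 77.7% starting point is already below the planned 80% for a separate reason: 100 is fewer than the plan's own 106. The better reason to change is that a source of bias can be removed cheaply, provided the sequence is concealed as well.

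**What to change.** 1. Keep consent, baseline measurements and the WOMAC at the office visit. Issue there a study number that has no link to the arm.
2. Assign the arm from a concealed random sequence, not odd/even order, after closure and the post-closure measurements, just before the garment is applied.
3. Count the 50 per group from that assignment. Report patients who consented but were not assigned separately, with reasons.

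**Cost.** Revised wording in Study Procedures; both garments at hand in the operating rooms used; assignment run there, which the team member already taking the post-closure measurements can do once the values are recorded; and a few more consents (6 to 12 under the assumed 5-10% loss). No extra visit is needed.

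**Limits.** This does not prevent withdrawal once the patient sees the garment, and it does not blind the assessments from day 1 onward. Those need their own provisions.

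### The trial is called randomised, but arms alternate by odd/even enrolment number with no concealment, so the next patient's arm can be foreseen at recruitment

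*Combined protocol and SAP*

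**What the plan says.** Study Design labels the trial a "Prospective randomized control cohort study". Study Procedures says that each patient is "assigned a unique study identifier which will be randomly assigned to the experimental or control group", and later that "The patient will then be placed in their randomized post-operative sleeve/device".

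The mechanism is set out in the same paragraph of Study Procedures. Identifiers begin at 1 and the series "will go up by one additional number with every patient enrolled in the study". Then: "Even numbers will be assigned to the control group and odd numbers will be assigned to the study group", to finish with 50 in each group. The identifier is issued at enrolment, after the baseline leg measurements, range of motion and WOMAC.

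Recruitment takes place at two offices (Setting: "Patients will be identified and recruited at office locations in Geauga and Beachwood, Ohio"). Under Consent Process, the patient is seen "behind closed doors with the performing surgeon and another member of the research team". REDCap is mentioned only as the place where data are recorded and stored. No section mentions a random sequence, envelopes, an independent allocator or central release of the assignment.

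**The concern.** The label and the mechanism contradict each other. Once the arm is the parity of an enrolment counter, nothing random remains, and patient 1 is fixed to the garment before recruitment opens.

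The practical harm is loss of concealment. The people who invite patients, judge eligibility and time the consent are the surgeon and the research team. If they know which arm comes next, that knowledge can affect who is enrolled and in what order. One exclusion criterion, inability to follow the standard post-operative and rehabilitation protocols, is a matter of judgement and so leaves room for this.

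Random allocation is what allows a garment-versus-stocking difference to be attributed to the garment. Without it, a difference could partly reflect who entered each arm, and selection in the opposite direction could hide a real benefit.

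**Working it through.** **1. The plan's own figure.** Identifiers 1 to 100 contain 50 odd and 50 even numbers, which reproduces the stated 50 per group. Parity alone therefore accounts for the whole allocation, and the plan needs no further random step to reach its arm sizes.

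**2. Predictability when all past numbers and arms are known.** Under the written rule, P(correct) = 1 for all 100 patients. For comparison, random lists of 100 were simulated with a recruiter who always guesses the arm that is behind, and guesses at random when the arms are level:

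| Method | Share guessed correctly |
|---|---|
| Odd/even rule | 100% |
| Fixed blocks of 4 | 71% |
| Varying blocks 2/4/6 | 70% |
| Varying blocks 4/6 | 69% |
| Varying blocks 4/6/8 | 68% |
| One random ordering of 50 and 50 | 56% |
| Unrestricted random list | 50% |

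**3. Predictability when only one's own office's numbers are known.** The documents give two offices and one number series. *Assumption:* the recruiter's office contributes a share p of patients, and the two offices' patients arrive in random order. The next own-office number has the opposite parity to the last one if an even number of other-office patients come in between. Hence

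P = p + p(1−p)² + p(1−p)⁴ + … = p / [1 − (1−p)²].

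- p = 0.5: 0.5 / 0.75 = 0.667
- p = 0.8: 0.8 / 0.96 = 0.833
- p = 0.2: 0.2 / 0.36 = 0.556

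The like-for-like figure for one varying-block list (p = 0.5, guessing the opposite of the last own-office arm) is about 57-59% by simulation.

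**4. Would the planned analysis catch or correct an imbalance?** The Data Analysis Plan tests baseline differences with t-tests. It switches to ANCOVA only if clinically relevant demographics differ significantly. The data list gives demographics as age, sex, weight, height and BMI. Read literally, a baseline difference in circumference, range of motion or WOMAC would not trigger adjustment at all.

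Even on a broader reading, the trigger has little power. For a two-sided t-test with 50 per arm, alpha 0.05 and 98 degrees of freedom, the noncentrality for a true imbalance of d SD is d × √(50/2) = 5d:

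| d (SD) | Noncentrality | P(significant) |
|---|---|---|
| 0.1 | 0.5 | 8% |
| 0.2 | 1.0 | 17% |
| 0.3 | 1.5 | 32% |
| 0.5 | 2.5 | 70% |

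A true imbalance of 0.2 SD would be flagged 17% of the time. Unmeasured traits, such as expected compliance, would never be flagged. The pain score, one of the primary outcomes, has no baseline value: in the Study Timeline table the row "Review of pain scale and narcotic use log" is first marked on post-operative day 1.

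**5. Illustration of the consequence.** The same table can be read the other way. *Assume* unmeasured selection shifts an outcome by 0.1, 0.2 or 0.3 SD when the garment has no effect. At the plan's pain SD of 2.5 these are 0.1 × 2.5 = 0.25, 0.2 × 2.5 = 0.5 and 0.3 × 2.5 = 0.75 points. The chance of a false positive in a planned t-test then rises from 5% to 8%, 17% or 32%. No passage supports any particular shift.

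**The case against.** The strongest reply is that the opportunity is narrower than it first looks. Patients agree to surgery before they are asked about the study, and consent follows scheduling, so the decision to operate cannot be steered by the next arm. Most eligibility criteria are objective. The documents do not say that the surgeon sees the running count, and with two offices on one series, certainty requires knowing the other office's enrolments. All of this is fair. It means that 100% applies to someone with the study-wide count and about 67% to someone without it. It does not create concealment: the documents do not offer the shared series as a safeguard, and the choice of whom to invite and when still comes before the number is issued.

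A second reply is that the false-positive rates come from assumed shifts and say nothing about this trial. That is right. They only show how sensitive a t-test with 50 per arm is to modest selection, and the finding does not depend on them.

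A third is that permuted blocks are also guessable when the devices are visible, and that a single random ordering of 50 and 50 would be less guessable (56%) and keep the arms exactly equal. This stands as a point about which random list to choose. It is no defence of alternation.

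Finally, the plan already issues the identifier after baseline measurement. That is true, but the weakness is that the arm can be known before that step.

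**Conclusion.** The concern holds, and this must be fixed. As written, the trial uses alternate allocation by enrolment order, contrary to its own description, with no concealment described. The next arm is known with certainty to anyone holding the study-wide count. It is guessable about 67% of the time from one office's numbers alone, or 56-83% for office shares of 20-80%, on the assumption of random arrival order.

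Whether selection would occur, and how large any bias would be, cannot be determined from the documents. What can be said is that the planned analysis would seldom detect a modest measured imbalance, may not adjust for one outside the listed demographics, and cannot address unmeasured selection.

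**What to change.** Replace the odd/even rule with a computer-generated 1:1 random sequence. Permuted blocks of varying size and a single random ordering of 50 and 50 are both acceptable. Someone not involved in recruitment should prepare and hold it, or it can be set up in the REDCap system already in use. Release each assignment only after consent, eligibility and baseline measurements are recorded, and use study numbers that carry no information about the arm. Site stratification is optional and is not needed to cure the defect.

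If any patients have already been allocated by parity, describe and report the trial as quasi-randomised by alternate allocation, and limit its causal conclusions accordingly.

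The cost is a short amendment, a one-off list and either one person outside recruitment or the REDCap set-up. There are no extra patients or visits. Because the devices are visible, blocks remain partly guessable. With varying blocks an incomplete last block may leave the arms at 49/51 or 48/52; exactly 50/50 occurred in 73-81% of simulated lists. The single 50/50 ordering avoids that.
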